4.4.5 Possible Anticipated Adverse Events and Clinical Monitoring

Anticipated AEs for which there will be specific safety monitoring in humans will be based on the preclinical studies as well as the published reports of studies of IL-10 protein injections to healthy volunteers. Potential for local injection site infection is very low since aseptic technique will be used and the investigators are highly trained and experienced in the administration of intra-articular injections.

[figure not shown]
Based on published reports of IL-10 protein injections in humans, the following AEs could be attributed to XT-150-produced IL-10var. IL-10 protein doses were more than 1000-fold higher than can be expected with XT-150.

- Minor decreases in neutrophils and T-lymphocytes.
- Changes in hemoglobin, platelet counts, and leukopenia
- Flu-like adverse effects related to IL-10, including symptoms of headache, and fever, chills, nausea, and myalgias, as reported by Chernoff (1995), Huhn (1996, 1997), and van Deventer (1997).

None of these AEs have been recorded for any of the patients in clinical studies following knee injections with XT-150 doses up to 600 µg, including 0201 study participants who received a second injection in the 0203 study.

[figure not shown]

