10.2 Adverse Events of Noted Interest in IL-10 Protein Trials

Safety will include the following reported IL-10 protein-associated toxicities as defined by Common Terminology Criteria for Adverse Events (CTCAE) criteria (version 5.0). Systemic levels of XT-150 produced IL-10 protein is expected to be more than 1000-fold lower than when given as a protein solution (Huhn 1997); and XT-150 will be predominately localized to the knee space.

- Grade 1 (unexplained) fever 38.6°C to 39°C
- Grade 2 allergic, cytokine release, or infusion-related reactions Therapy or infusion interruption indicated but responds promptly to symptomatic treatment (e.g., antihistamines, NSAIDS, narcotics, IV fluids); prophylactic medications indicated for ≤24 hours
- Grade 2 injection site reaction Pain; lipodystrophy; edema; phlebitis
- Grade 2 neutropenia <1500 to $1000/\text{mm}^3$; <1.5 to $1.0 \times 10^9/\text{L}$

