10.5 Definitions

10.5.1 Adverse Event

An AE means any untoward medical occurrence associated with the use of a drug in humans, whether or not considered drug related. An AE (also referred to as an adverse experience) can be any unfavorable and unintended sign (e.g., a clinically significant abnormal laboratory finding), symptom, or disease temporally associated with the use of a drug, and does not imply any judgment about causality. An AE can arise with any use of the drug and with any route of administration, formulation, or dose, including an overdose.

Osteoarthritis-related events should not be considered or recorded as AEs unless the event fits the definition for an SAE (Section 10.5.4), in which case the SAE form must be submitted for safety reporting in the appropriate timeframe and entered as an AE into the CRF.

Laboratory abnormalities should not be recorded as AEs or SAEs unless they are associated with clinical signs or symptoms, or require medical intervention. However, each laboratory abnormality (e.g., clinically significant changes detected on hematology, or lab chemistries) independent from any underlying medical condition that requires

medical or surgical intervention, or that leads to interruption of study drug infusion or discontinuation, must be recorded as an AE, or SAE if applicable. If the laboratory abnormality is part of a clinical condition or syndrome, it should be recorded as the syndrome or diagnosis rather than as the individual laboratory abnormality. In addition, laboratory abnormalities or other abnormal test assessments that are associated with signs or symptoms must be recorded as AEs or SAEs if they meet the definition of an AE (or SAE) as described above or in Section 10.5.4.

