10.6.2 Severity

All AEs will be graded for severity to describe the maximum intensity of the AE based on Common Terminology Criteria for Adverse Events (CTCAE) criteria (version 5.0). For purposes of consistency, these intensity grades are defined in Table 6.

Table 6. Guidelines for Severity Assessments

Grade 1	Mild; asymptomatic or mild symptoms; clinical or diagnostic observations only; intervention not indicated
Grade 2	Moderate; minimal, local or non-invasive intervention indicated; limiting age-appropriate instrumental activities of daily living (e.g., preparing meals, shopping for groceries or clothes, using the telephone, managing money)
Grade 3	Severe or medically significant but not immediately life-threatening; hospitalization or prolongation of hospitalization indicated; disabling; limiting self-care activities of daily living (bathing, dressing and undressing, feeding self, using the toilet, taking medications, and not bedridden)
Grade 4	Life-threatening consequences; urgent intervention indicated
Grade 5	Death related to adverse event

These criteria, in addition to good clinical judgment, should be used as a guide for determining the causal assessment. If the event is believed to be unrelated to study drug administration, then an alternative explanation should be provided.

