#### 5.5. Data Derived by Calculation

The following data fields for inclusion in the data listings will be derived by calculation as per the Clinical Data Interchange Standards Consortium (CDISC) standard:

Adverse Events:

• Treatment for adverse event, assigned as

```
Non-Treatment-Emergent if (Onset Date) < (Date of Stage A Dose)
```

[figure not shown]
Treatment for Stage A if
(Onset Date) >= (Date of Stage A Dose) &
(Onset Date) < (Date of Stage B Dose);

Treatment for Stage B if (Onset Date) >= (Date of Stage B Dose)

CONFIDENTIAL Page 12 of 27

Protocol No.: XT-150-2-0204 Sponsor: Xalud Therapeutics, Inc.

- Adverse event time since Stage B dose (in days), calculated as
   (Onset Date) (Date of Stage B Dose) if (Onset Date) >= (Date of Stage B
   Dose)
- Adverse event time since Stage B dose is Not Applicable if if (Onset Date) < (Date of Stage B Dose)

- Adverse event duration (in days), calculated as (Resolution Date

  – Onset Date)

Safety Assessments Change from Baseline:

Baseline for vital signs and clinical laboratory parameters will be the most recent
assessment prior to first dose [which may be an unscheduled assessment, a repeat of
a scheduled Baseline assessment, or the screening assessment if separate Baseline
assessments are not performed]

Clinical Safety Laboratory Assessments:

- If a clinical laboratory result is above the upper limit of normal, then Out of Range flag will be set to "H"
- If a clinical laboratory result is below the lower limit of normal, then Out of Range flag will be set to "L"
- Clinical Laboratory parameters that are outside the reference range and medically assessed as clinically significant will be identified as "Abnormal CS"
- Clinical Laboratory parameters that are outside the reference range and not medically assessed as clinically significant will be identified as "Abnormal NCS"

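### A Grade 2 neutrophil count is a named safety event, but the AE recording rule can keep it out of the AE tables, and no graded laboratory table is visible in their place

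*Protocol*

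**What the plan says.** Protocol 10.2 deals with adverse events of noted interest. It states: "Safety will include the following reported IL-10 protein-associated toxicities as defined by Common Terminology Criteria for Adverse Events (CTCAE) criteria (version 5.0"). Four items follow, one of which is "Grade 2 neutropenia <1500 to" 1000/mm³. That item is a count band, with no symptom or treatment element. Protocol 4.4.5 lists "Minor decreases in neutrophils and T-lymphocytes" among the AEs that might be attributed to the IL-10 variant that XT-150 produces.

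Protocol 10.5.1 pulls in more than one direction:

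- The opening definition of an AE covers "any unfavorable and unintended sign (e.g., a clinically significant abnormal laboratory finding").
- A later paragraph says "Laboratory abnormalities should not be recorded as AEs or SAEs unless they are associated with clinical signs or symptoms, or require medical intervention".
- The next sentence adds that an abnormality needing medical or surgical intervention, "or that leads to interruption of study drug infusion or discontinuation, must be recorded as an AE, or SAE if applicable".

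The visible text contains no exception for the toxicities listed in 10.2.

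Protocol 13.4 and SAP 8.2 build the AE tables from recorded treatment-emergent AEs. For laboratory data, 13.4 promises incidences of potentially clinically significant results and leaves their definition to the SAP. SAP 5.5 sets out a high/low flag ("If a clinical laboratory result is below the lower limit of normal, then Out of Range flag will be set to" L) and a medical call of clinically significant (CS) or not (NCS). SAP 8.2 lists hematology and summarizes results, changes from baseline and medical assessments by treatment group and time point. Individual profiles are produced for parameters with a post-dose value out of range and judged clinically significant.

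**The concern.** Safety and tolerability are the primary objective (protocol 5.0). Section 10.2 singles out a laboratory-defined event for evaluation, and 10.5.1 then sets a general recording rule that can keep that event out of the AE dataset. If the rule is applied as written, the neutropenia row of the TEAE table reflects which low counts happened to come with symptoms, treatment or discontinuation. It does not show how many participants reached Grade 2. A reader of the study report who sees few or no cases there would be tempted to take that as evidence about the toxicity.

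The second risk is inconsistency. Because the opening definition and the later paragraph of 10.5.1 differ, one investigator may enter a low count as an AE and another may not. With about 5 planned centers, differences in site practice could affect the tabulated number.

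**Working it through.** The plan states no figure on this point, so there is nothing to reproduce. The check follows one hypothetical value, a Day 60 neutrophil count of 1200/mm³ in a participant without symptoms, through the text.

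1. **Is it the 10.2 event?** 1000 ≤ 1200 < 1500, so it lies in the Grade 2 band. Nothing else is required.

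2. **Is it recorded under 10.5.1?** There are no signs or symptoms and no intervention, so the later paragraph says not to record it. Three possible ways back in:
   - *Interruption or discontinuation.* Stage A treatment is one injection on Day 0, and protocol 7.4.2 anticipates no discontinuation apart from problems in the 24 hours before dosing. The only scheduled post-dose blood count in the visible schedule is at Day 60 (Table 1 and section 9.5), after that injection has been given. In practice this ground could bear only on study withdrawal or on the optional later injection.
   - *Severity wording.* Table 6 describes Grade 2 generically as "Moderate; minimal, local or non-invasive intervention indicated". One could argue that every Grade 2 event therefore calls for intervention, but 10.2 defines this item by count alone, and a count does not show that intervention was required.
   - *Clinical significance.* An investigator who judges 1200/mm³ clinically significant can rely on the opening definition and record it. Another who follows the later paragraph would not. The text supports both.

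3. **Does it reach the TEAE tables?** Only if it was recorded (protocol 13.4, SAP 8.2). Otherwise it does not.

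4. **Does the laboratory route count it?** It is listed. If the laboratory's lower limit is 1500/mm³ or higher, it is flagged L and then classed CS or NCS. Neither class matches the 10.2 event. With a lower limit above 1500, the L flag also takes in counts that are not Grade 2. The CS class keeps only those that a clinician chose to call significant. The visible SAP text gives no count threshold for the results that 13.4 refers to it, and no tabulation by CTCAE grade.

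5. **Scope.** Of the four 10.2 items, fever, allergic or infusion-type reaction, and injection site reaction are clinical events. Only neutropenia is defined by a laboratory value: 1 of 4.

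6. **Number of cases.** The documents give no rate of Grade 2 neutropenia and no share that would be symptom-free and untreated. As an unanchored illustration of scale only, with 2 × 90 = 180 participants on XT-150, assumed rates of 1%, 3% and 5% give 180 × 0.01 = 1.8, 180 × 0.03 = 5.4 and 180 × 0.05 = 9.0 counts in the band. This assumes that everyone has a Day 60 sample, and it says nothing about an excess over placebo.

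7. **What a Day 60 count can show.** Exclusion criterion 12 bars neutrophils below 1500/mm³, so a lower Day 60 value is new relative to screening. Screening may be up to 30 days before enrollment and no blood count is scheduled on Day 0, so the value is not proven to be new relative to dosing. That is why the placebo group belongs in any tabulation.

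**The case against.** The strongest defense is that laboratory data are a separate safety stream by design. Protocol 10.1 assesses safety through AEs, vital signs and laboratory data. Section 10.2 says that safety will include these toxicities, not that each must become an AE record. Keeping isolated laboratory values out of the AE tables and reporting them in laboratory tables is a legitimate choice, and 13.4 commits to counting potentially clinically significant results whatever was recorded as an AE. Most of this stands. It moves the question to whether the laboratory stream counts the event that 10.2 names, and the visible text does not show that it does.

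Three stronger readings are tempting, and the documents do not support them.

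- A reader might infer that recording a symptom-free low count is prohibited outright. It is not: intervention, interruption and discontinuation all require recording, and the AE definition itself cites a clinically significant laboratory finding.
- A reader might infer that the event vanishes from the report. It does not: hematology is listed, flagged and summarized by group. Nor can the absence of a graded table be asserted, because the planned listings and tables (SAP Appendices 1 and 2) are blank in the public copy.
- A reader might infer that a particular number of cases would be missed, or that the AE table would show zero. No rate in the documents supports this. Protocol 4.4.5 points the other way: no such AEs were recorded at doses up to 600 µg, and the published IL-10 protein doses were more than 1000-fold above what is expected here.

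**Conclusion.** The point holds as a minor but real inconsistency. Sections 10.2 and 10.5.1 are not reconciled, and 10.5.1 is not consistent within itself on clinically significant laboratory findings. A Grade 2 count without symptoms, intervention, interruption or discontinuation can be left out of the TEAE tables, so a low or zero neutropenia figure there would not establish that the toxicity was absent.

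It affects one of four listed items, and its effect in cases is unknown. The conclusion rests on two assumptions: that sites follow the later paragraph of 10.5.1, and that no exception for the 10.2 list sits in text missing from the public copy. The weaker statement about the laboratory outputs, that no graded neutrophil table is visible, would fall away if the redacted table list contains one.

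**What to change.** Preferred: in SAP 8.2, grade the post-dose (Day 60) neutrophil counts by CTCAE v5.0 and tabulate the number and percentage of participants at Grade 2 or higher by treatment group, including placebo, with the number who had a Day 60 sample as denominator. The same paragraph can supply, for neutrophils, the definition that protocol 13.4 leaves to the SAP. If such a table is already planned, citing it next to 10.2 is enough. This uses blood counts already scheduled and costs one extra table.

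Alternative: add a sentence to protocol 10.5.1 stating that events listed in 10.2 are recorded as AEs regardless of symptoms. This costs a protocol change and a small extra recording burden at sites.

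Under either route, the opening definition and the later laboratory paragraph of 10.5.1 should be reconciled so that sites treat the same count in the same way.

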10.5.2 Suspected Adverse Drug Reaction

A suspected adverse drug reaction is any AE for which there is a reasonable possibility that the drug caused the AE. For the purposes of Investigational New Drug safety reporting, "reasonable possibility" means there is evidence to suggest a causal relationship between the drug and the AE. Suspected adverse drug reaction implies a lesser degree of certainty about causality than adverse reaction, which means any AE caused by a drug.

10.5.3 Life-Threatening AE or Life-Threatening Suspected Adverse Drug Reaction

An AE or suspected adverse drug reaction is considered "life threatening" if, in the view of either the Investigator or Sponsor, its occurrence places the patient or participant at immediate risk of death. It does not include an AE or suspected adverse reaction that, had it occurred in a more severe form, might have caused death.

10.5.4 Serious AE or Serious Suspected Adverse Reaction

An AE or suspected adverse reaction is considered "serious" if, in the view of either the Investigator or Sponsor, it results in any of the following outcomes:

- Death
- A life-threatening AE see definition above
- Inpatient hospitalization or prolongation of existing hospitalization
- A persistent or significant incapacity or substantial disruption of the ability to conduct normal life functions
- Congenital anomaly/birth defect in the offspring of a participant who received study drug

Important medical events that may not result in death, be life-threatening, or require hospitalization may be considered serious when, based upon appropriate medical judgment, they may jeopardize the patient or participant and may require medical or surgical intervention to prevent one of the outcomes listed in this definition. Examples of such medical events include allergic bronchospasm requiring intensive treatment in an emergency room or at home, blood dyscrasias, or convulsions that do not result in inpatient hospitalization, or the development of drug dependency or drug abuse.

10.5.5 Unexpected AE or Unexpected Suspected Adverse Drug Reaction

An AE or suspected adverse drug reaction is considered "unexpected" if:

• It is not listed in the Investigator's Brochure or is not listed at the specificity or severity that has been observed

For example, under this definition, hepatic necrosis would be unexpected (by virtue of greater severity) if an Investigator's Brochure referred only to elevated hepatic enzymes or hepatitis. Similarly, cerebral thromboembolism and cerebral vasculitis would be unexpected (by virtue of greater specificity) if an Investigator's Brochure listed only cerebral vascular accidents.

"Unexpected," as used in this definition, also refers to AEs or suspected adverse reactions that are mentioned in the Investigator's Brochure as occurring with a class of drugs or as anticipated from the pharmacological properties of the drug, but are not specifically mentioned as occurring with the particular drug under investigation.

10.6 Adverse Event Classification

10.6.1 Relationship to Investigational Drug

The Investigator's assessment of causality must be provided for all AEs (serious and non-serious) (Table 5). An Investigator's causality assessment is the determination of whether there exists a reasonable possibility that the study drug caused or contributed to an AE. Clinical failure that qualifies as an AE without evidence of study drug toxicity should be considered unrelated to study drug.

Table 5. Guidelines for Assessing Relationship of Event to Study Drug

Unrelated	There is little or no chance that the Investigational Product caused the AE; other conditions, including concurrent illnesses, progression or expression of the disease state, or a reaction to a concomitant medication best explain the event
Related	The association of the AE with the Investigational Product is unknown, however, the AE is not clearly due to another condition, or a reasonable temporal association exists between the AE and treatment administration and, based on the Investigator's clinical experience, the association of the AE with the Investigational Product seems likely

AE = adverse event

10.6.2 Severity

All AEs will be graded for severity to describe the maximum intensity of the AE based on Common Terminology Criteria for Adverse Events (CTCAE) criteria (version 5.0). For purposes of consistency, these intensity grades are defined in Table 6.

Table 6. Guidelines for Severity Assessments

Grade 1	Mild; asymptomatic or mild symptoms; clinical or diagnostic observations only; intervention not indicated
Grade 2	Moderate; minimal, local or non-invasive intervention indicated; limiting age-appropriate instrumental activities of daily living (e.g., preparing meals, shopping for groceries or clothes, using the telephone, managing money)
Grade 3	Severe or medically significant but not immediately life-threatening; hospitalization or prolongation of hospitalization indicated; disabling; limiting self-care activities of daily living (bathing, dressing and undressing, feeding self, using the toilet, taking medications, and not bedridden)
Grade 4	Life-threatening consequences; urgent intervention indicated
Grade 5	Death related to adverse event

These criteria, in addition to good clinical judgment, should be used as a guide for determining the causal assessment. If the event is believed to be unrelated to study drug administration, then an alternative explanation should be provided.

10.6.3 Serious Adverse Event

Any adverse experience occurring at any dose of study medication that occurs between the time of informed consent and the clinic visit on Day 360 that results in any of the following outcomes:

- Death
- Life-threatening situation (participant is at immediate risk of death)
- Inpatient hospitalization or prolongation of existing hospitalization
- Persistent or significant disability/incapacity
- Congenital anomaly/birth defect in the offspring of a participant who received study drug
- Events that jeopardize the participant sufficiently that medical or surgical intervention may be required to prevent one of the above outcomes. Examples may include, but are not limited, to:
 - Intensive treatment in an emergency room or at home for allergic bronchospasm
 - O Blood dyscrasias that do not result in hospitalization
 - Seizures that do not result in hospitalization

10.6.3.1 Serious Adverse Event Definition Clarifications

- Death is an outcome of an AE, and not an AE in itself
- All deaths during study drug administration or up to the FU visit on Day 90, regardless of cause or relationship, must be reported
- "Occurring at any dose" does not imply that the participant is actively receiving study drug at the time of the event
- "Life-threatening" means that the participant was at immediate risk of death from the event as it occurred. This does not include an event that might have led to death, had it occurred with greater severity.
- Complications that occur during hospitalizations are AEs. If an AE prolongs hospitalization, it is an SAE.
- "Inpatient hospitalization" means the participant has been formally admitted to a hospital for medical reasons, for any length of time. This may or may not be overnight. It does not include presentation and care within an emergency department (although an emergency department visit may define a medically important event, which is also considered an SAE).
- The Investigator should attempt to establish a diagnosis of the event based on signs, symptoms, and other clinical information. In such cases, the diagnosis should be documented as the AE or SAE, rather than as the individual signs or symptoms.

